7.2 Dose Modification (Escalation/Titration/Other)

7.2.1 Dose Modification and Toxicity Management Guidelines for Pembrolizumab

Dose Modification and Toxicity Management for Immune-related Adverse Events Associated With Pembrolizumab

AEs associated with pembrolizumab exposure may represent an immunologic etiology. These irAEs may occur shortly after the first dose or several months after the last dose of pembrolizumab treatment and may affect more than one body system simultaneously. Therefore, early recognition and initiation of treatment is critical to reduce complications. Based on existing clinical trial data, most irAEs were reversible and could be managed with interruptions of pembrolizumab, administration of corticosteroids, and/or other supportive care. For suspected irAEs, ensure adequate evaluation to confirm etiology or exclude other causes. Additional procedures or tests such as bronchoscopy, endoscopy, or skin biopsy may be included as part of the evaluation. Based on the severity of irAEs, withhold or permanently discontinue pembrolizumab and administer corticosteroids. Dose modification and toxicity management guidelines for irAEs associated with pembrolizumab are provided in [Table 5](#).

Table 5 Dose Modification and Toxicity Management Guidelines for Immune-related Adverse Events Associated With Pembrolizumab

General instructions:				

 1. Corticosteroid taper should be initiated upon AE improving to Grade 1 or less and continue to taper over at least 4 weeks. 2. For situations where pembrolizumab has been withheld, pembrolizumab can be resumed after AE has been reduced to Grade 1 or 0 and corticosteroid has been tapered. Pembrolizumab should be permanently discontinued if AE does not resolve within 12 weeks of last dose or corticosteroids cannot be reduced to ≤ 10 mg prednisone or equivalent per day within 12 weeks. 3. For severe and life-threatening irAEs, IV corticosteroids should be initiated first, followed by oral steroids. Other immunosuppressive treatment should be initiated if irAEs cannot be controlled by corticosteroids. 				
Immune-related AEs	Toxicity grade or conditions (CTCAEv4.0)	Action taken to pembrolizumab	irAE management with corticosteroid and/or other therapies	Monitor and follow-up
Pneumonitis	Grade 2	Withhold	
 • Administer corticosteroids (initial dose of 1-2 mg/kg prednisone or equivalent) followed by taper 	
 • Monitor participants for signs and symptoms of pneumonitis • Evaluate participants with suspected pneumonitis with radiographic imaging and initiate corticosteroid treatment • Add prophylactic antibiotics for opportunistic infections
	Grade 3 or 4, or recurrent Grade 2	Permanently discontinue		
Diarrhea / colitis	Grade 2 or 3	Withhold	
 • Administer corticosteroids (initial dose of 1-2 mg/kg prednisone or equivalent) followed by taper 	
 • Monitor participants for signs and symptoms of enterocolitis (ie, diarrhea, abdominal pain, blood or mucus in stool with or without fever) and of bowel perforation (ie, peritoneal signs and ileus). • Participants with \geqGrade 2 diarrhea suspecting colitis should consider gastrointestinal consultation and performing endoscopy to rule out colitis. • Participants with diarrhea/colitis should be advised to drink liberal quantities of clear fluids. If sufficient oral fluid intake is not feasible, fluid and electrolytes should be substituted via IV infusion.
	Grade 4	Permanently discontinue		

Immune-related AEs	Toxicity grade or conditions (CTCAEv4.0)	Action taken to pembrolizumab	irAE management with corticosteroid and/or other therapies	Monitor and follow-up
AST / ALT elevation or increased bilirubin	Grade 2	Withhold	
 Administer corticosteroids (initial dose of 0.5-1 mg/kg prednisone or equivalent) followed by taper 	
 Monitor with liver function tests (consider weekly or more frequently until liver enzyme value returned to baseline or is stable)
	Grade 3 or 4	Permanently discontinue	
 Administer corticosteroids (initial dose of 1-2 mg/kg prednisone or equivalent) followed by taper 	
T1DM or hyperglycemia	Newly onset T1DM or Grade 3 or 4 hyperglycemia associated with evidence of β -cell failure	Withhold	
 Initiate insulin replacement therapy for participants with T1DM Administer antihyperglycemic in participants with hyperglycemia 	
 Monitor participants for hyperglycemia or other signs and symptoms of diabetes
Hypophysitis	Grade 2	Withhold	
 Administer corticosteroids and initiate hormonal replacements as clinically indicated 	
 Monitor for signs and symptoms of hypophysitis (including hypopituitarism and adrenal insufficiency)
	Grade 3 or 4	Withhold or permanently discontinue ^a		
Hyperthyroidism	Grade 2	Continue	
 Treat with nonselective beta-blockers (eg, propranolol) or thionamides as appropriate 	
 Monitor for signs and symptoms of thyroid disorders
	Grade 3 or 4	Withhold or Permanently discontinue ^a		
Hypothyroidism	Grade 2-4	Continue	
 Initiate thyroid replacement hormones (eg, levothyroxine or liothyronine) per standard of care 	
 Monitor for signs and symptoms of thyroid disorders
Nephritis and renal dysfunction	Grade 2	Withhold	
 Administer corticosteroids (prednisone 1-2 mg/kg or equivalent) followed by taper 	
 Monitor changes of renal function
	Grade 3 or 4	Permanently discontinue		

Immune-related AEs	Toxicity grade or conditions (CTCAEv4.0)	Action taken to pembrolizumab	irAE management with corticosteroid and/or other therapies	Monitor and follow-up
Myocarditis	Grade 1 or 2	Withhold	
 Based on severity of AE administer corticosteroids 	
 Ensure adequate evaluation to confirm etiology and/or exclude other causes
	Grade 3 or 4	Permanently discontinue		
All Other immune-related AEs	Intolerable/persistent Grade 2	Withhold	
 Based on severity of AE administer corticosteroids 	
 Ensure adequate evaluation to confirm etiology or exclude other causes
	Grade 3	Withhold or discontinue based on the type of event. Events that require discontinuation include and not limited to: Guillain-Barre Syndrome, encephalitis		
	Grade 4 or recurrent Grade 3	Permanently discontinue		

AE=adverse event; ALT=alanine aminotransferase; AST=aspartate aminotransferase; CTCAE=Common Terminology Criteria for Adverse Events; irAE=immune-related adverse event; IV=intravenous; T1DM= Type 1 diabetes mellitus.

a. Withhold or permanently discontinue pembrolizumab is at the discretion of the investigator or treating physician.

NOTE: For participants with Grade 3 or 4 immune-related endocrinopathy where withhold of pembrolizumab is required, pembrolizumab may be resumed when AE resolves to \leq Grade 2 and is controlled with hormonal replacement therapy or achieved metabolic control (in case of T1DM).

Dose Modification and Toxicity Management of Infusion Reactions Related to Pembrolizumab

Pembrolizumab may cause severe or life-threatening infusion reactions including severe hypersensitivity or anaphylaxis. Signs and symptoms usually develop during or shortly after drug infusion and generally resolve completely within 24 hours of completion of infusion. Dose modification and toxicity management guidelines on pembrolizumab-associated infusion reaction are provided in [Table 6](#).

Table 6 Pembrolizumab Infusion Reaction Dose Modification and Treatment Guidelines

NCI CTCAE Grade	Treatment	Premedication at Subsequent Dosing

Grade 1 Mild reaction; infusion interruption not indicated; intervention not indicated
	
Increase monitoring of vital signs as medically indicated until the participant is deemed medically stable in the opinion of the investigator.
	
None

Grade 2 Requires therapy or infusion interruption, but responds promptly to symptomatic treatment (eg, antihistamines, NSAIDs, narcotics, IV fluids); prophylactic medications indicated for ≤24 h
	
Stop Infusion. Additional appropriate medical therapy may include, but is not limited to: IV fluids Antihistamines NSAIDs Acetaminophen Narcotics Increase monitoring of vital signs as medically indicated until the participant is deemed medically stable in the opinion of the investigator. If symptoms resolve within 1 hour of stopping drug infusion, the infusion may be restarted at 50% of the original infusion rate (eg, from 100 mL/h to 50 mL/h). Otherwise dosing will be held until symptoms resolve and the participant should be premedicated for the next scheduled dose. Participants who develop Grade 2 toxicity despite adequate premedication should be permanently discontinued from further study treatment
	
Participant may be premedicated 1.5 h (±30 minutes) prior to infusion of pembrolizumab with: Diphenhydramine 50 mg po (or equivalent dose of antihistamine). Acetaminophen 500-1000 mg po (or equivalent dose of analgesic).

NCI CTCAE Grade	Treatment	Premedication at Subsequent Dosing

Grades 3 or 4 Grade 3: Prolonged (ie, not rapidly responsive to symptomatic medication and/or brief interruption of infusion); recurrence of symptoms following initial improvement; hospitalization indicated for other clinical sequelae (eg, renal impairment, pulmonary infiltrates) Grade 4: Life-threatening; pressor or ventilatory support indicated
	
Stop Infusion. Additional appropriate medical therapy may include, but is not limited to: Epinephrine** IV fluids Antihistamines NSAIDs Acetaminophen Narcotics Oxygen Pressors Corticosteroids Increase monitoring of vital signs as medically indicated until the participant is deemed medically stable in the opinion of the investigator. Hospitalization may be indicated. **In cases of anaphylaxis, epinephrine should be used immediately. Participant is permanently discontinued from further study treatment.
	
No subsequent dosing

IV=intravenous; NCI CTCAE=National Cancer Institute Common Terminology Criteria for Adverse Events; NSAID=nonsteroidal anti-inflammatory drug; po=per os (orally). Appropriate resuscitation equipment should be available at the bedside and a physician readily available during the period of drug administration. For further information, please refer to the Common Terminology Criteria for Adverse Events v4.0 (CTCAE) at http://ctep.cancer.gov
		

Other Allowed Dose Interruption for Pembrolizumab

Pembrolizumab may be interrupted for situations other than treatment-related AEs such as medical / surgical events or logistical reasons not related to study treatment. Participants should be placed back on study treatment within 3 weeks of the scheduled interruption, unless otherwise discussed with the Sponsor. The reason for interruption should be documented in the participant’s study record.

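### Table 5 lists Grade 1 as a hold grade for myocarditis, while its general rule permits resumption after a fall to Grade 1 with steroids tapered

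*Combined protocol and SAP*

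**What the plan says.** Table 5 in protocol Section 7.2.1 opens with general instructions and then gives event-specific rows.

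- **Instruction 2, resumption.** It begins "For situations where pembrolizumab has been withheld", so it covers every hold in the table. It then says that "pembrolizumab can be resumed after AE has been reduced to Grade 1 or 0 and corticosteroid has been tapered". Both parts must be met: the grade and the taper.
- **Instruction 2, time limit.** "Pembrolizumab should be permanently discontinued if AE does not resolve within 12 weeks of last dose". A parallel limit applies if steroids cannot be brought down far enough in 12 weeks.
- **Instruction 1, steroids.** "Corticosteroid taper should be initiated upon AE improving to Grade 1 or less and continue to taper over at least 4 weeks".
- **Myocarditis row.** "Myocarditis Grade 1 or 2 Withhold", with permanent discontinuation at Grade 3 or 4. On steroids the row says only "Based on severity of AE administer corticosteroids".
- **Note under the table.** The one event-specific resume rule begins "For participants with Grade 3 or 4 immune-related endocrinopathy where withhold of pembrolizumab is required". It is limited to endocrine events.

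**The concern.** A hold-and-resume scheme works when the grades that trigger a hold and the grades that allow a restart do not overlap. Here they share Grade 1 for one event, and the table does not say which line prevails.

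The consequence is clinical first. Two sites with the same participant, whose myocarditis has fallen from Grade 2 to Grade 1 and whose steroids are tapered, could act differently and each point to Table 5. One would re-expose the participant and the other would continue the hold. A continued hold can also run into the 12-week limit, and under Section 8.1 a discontinuation cannot be reversed. To that extent, the reading a site adopts could change whether a participant is counted as discontinued due to an AE.

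**Working it through.** No arithmetic in the plan bears on this. The check compares the grades that trigger a hold in each row with the grades that satisfy instruction 2, and then looks for any text that settles the overlap.

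**Step 1. Hold grades against resume grades.** The resume grades under instruction 2 are 0 and 1.

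| Table 5 row | Grades with a hold | Overlap with 0 or 1 |
|---|---|---|
| Pneumonitis | 2 | none |
| Diarrhea/colitis | 2, 3 | none |
| AST/ALT or bilirubin | 2 | none |
| T1DM or hyperglycemia | hyperglycemia 3, 4; new T1DM (ungraded) | none among graded triggers |
| Hypophysitis | 2; 3 and 4 (hold or stop, by discretion) | none |
| Hyperthyroidism | 3 and 4 (hold or stop, by discretion) | none |
| Hypothyroidism | no hold | none |
| Nephritis | 2 | none |
| Myocarditis | 1, 2 | **Grade 1** |
| All other immune-related AEs | 2 if intolerable or persistent; 3 (hold or stop, by event type) | none |

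Myocarditis is the only graded row with an overlap.

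**Step 2. Grade 2 falling to Grade 1, steroids tapered.** Under instruction 2 the grade has been reduced to 1 and the taper condition is met, so resumption is permitted. Under the row, Grade 1 is a hold grade. The two lines point in different directions.

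**Step 3. Onset at Grade 1.** The row calls for a hold. Instruction 2 requires that the AE has been *reduced to* Grade 1 or 0. An event that began at Grade 1 has not been reduced to Grade 1. Read literally, the condition is met only at Grade 0, but the text does not say so. The resume point is unsettled rather than contradictory.

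**Step 4. Text in Section 7 and Section 2 that might settle it.**

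- The endocrinopathy note does not reach myocarditis.
- Footnote a, which gives the investigator discretion, is attached only to hypophysitis and hyperthyroidism.
- The taper condition carries no grade. Because the row ties steroids to severity, the condition may be empty if none are given at Grade 1.
- The 12-week limit uses *resolve* without a grade. Elsewhere the word is paired with different grades: 0 to 1 in the AE monitoring note of the Schedule of Activities, and Grade 2 or below in the endocrinopathy note.
- Sponsor consultation on interruptions beyond 3 weeks (Section 7.2.1, other allowed interruptions, and Section 7.6) concerns reasons other than treatment-related AEs.

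None of these gives a resume grade for myocarditis.

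**The case against.** The best answer is that the two lines do different jobs. The row gives the action when the event appears, and instruction 2 governs what follows a hold. On that view a Grade 2 event that falls to Grade 1 is simply under instruction 2. This is a plausible reading, but the table does not state it. Instruction 2 is also permissive: drug *can* be resumed, so a longer hold is compliant in any row, and some variation between sites is built in. That narrows the conflict. It does not say whether resuming at Grade 1 is acceptable in the one row where Grade 1 itself calls for a hold.

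There is also a safeguard outside Table 5. Appendix 4 requires advance approval by the sponsor's clinical director before rechallenge if the AE was serious and may have been caused by the product, or if re-exposure carries additional potential significant risk. Section 8.1 lets the investigator or sponsor stop treatment where continuing would put the participant at unnecessary risk. These provisions may well catch some myocarditis cases, and where Appendix 4 applies, a site that resumed alone would not be compliant. But they do not cover every Grade 1 or 2 event, they give no grade criterion, and the Appendix 4 rule refers back to the dose modification guidelines.

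A reader might go further and infer that an event starting at Grade 1 already satisfies the resume rule, or sits at the steroid taper point from the outset. The documents do not support this. Instruction 1 starts the taper "Corticosteroid taper should be initiated upon AE improving to Grade 1 or less" (my point is the verb: the AE must improve), and instruction 2 likewise requires a reduction and a completed taper condition.

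**Conclusion.** The point holds in a limited form. For Grade 2 myocarditis that improves to Grade 1 with steroids tapered, two stated safety instructions conflict. For myocarditis that starts at Grade 1, the resume point is not settled. This is an internal inconsistency in clinical management text, and the passages need to be reconciled. This review takes no view on which criterion is right.

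Its size is small but cannot be put in numbers. The documents give no incidence of myocarditis; cases are probably few. Section 10.9 suggests that randomization is complete, and the documents do not say how many participants are still on treatment. DFS, OS, alpha and power are not affected.

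Two further inferences are tempting and should not be drawn.

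- **That the Dose Interruption row of Table 12 would change.** Instruction 2 applies only after drug has been withheld, so the participant has had an interruption under either reading, and the row counts participants. Only the discontinuation row could differ, through the 12-week limit. Both rows are Tier 3 and descriptive.
- **That a continued hold costs 12/3 = 4 of the 17 doses.** The resolution clock runs from the last dose. Resuming at week 12 misses the doses due at weeks 3, 6 and 9, which is three. If the AE has not resolved by then, all remaining doses are lost. Where steroids are used, the taper of at least 4 weeks delays dosing under both readings. The documents therefore support no single figure for the difference.

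**What to change.** The sponsor should reconcile the myocarditis row of Table 5 with general instructions 1 and 2 and with the rechallenge provision in Appendix 4. One line in the row, or a note like the existing endocrinopathy note, would do. It should state which resume criterion and which taper criterion apply to myocarditis, cover both a Grade 2 event that has fallen to Grade 1 and an event that starts at Grade 1, and say how Appendix 4 approval fits in. The sponsor's safety group should choose the criterion.

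The cost is one line, by amendment or protocol clarification letter, with no added procedures or data collection and no change to the statistical analysis. The practical benefit depends on how many participants are still receiving study treatment when it is issued.

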7.3 Method of Treatment Assignment

All eligible participants will be randomly allocated and will receive a treatment/randomization number. The treatment/randomization number identifies the participant for all procedures occurring after treatment allocation/randomization. Once a treatment/randomization number is assigned to a participant, it can never be re-assigned to another participant.

A single participant cannot be assigned more than 1 treatment/randomization number.

Treatment allocation/randomization will occur centrally using the IVRS/IWRS. There are 2 study treatment arms. Participants will be assigned randomly in a 1:1 ratio to either:

- Pembrolizumab monotherapy
- Placebo (carrier solution only)

7.3.1 Stratification

Treatment allocation/randomization will be stratified according to the following factors:

Metastasis status (M0 versus M1 NED)

Within M0 group, there will be 2 stratification factors:

- a. ECOG PS (0 versus 1)
- b. US participant (YES versus NO)

7.4 Blinding

A double-blinding technique will be used. MK-3475 and placebo will be prepared and/or dispensed in a blinded fashion by an unblinded pharmacist or qualified trial site personnel. The participant and the investigator who is involved in the study treatment administration or clinical evaluation of the participants are unaware of the group assignments.

See Section 9.1.10 for a description of the method of unblinding a participant during the trial, should such action be warranted.

7.5 Preparation/Handling/Storage/Accountability

7.5.1 Dose Preparation

Details on preparation and administration of pembrolizumab are provided in the Pharmacy Manual.

The rationale for selection of doses to be used in this trial is provided in Section 5.5. There are no specific calculations or evaluations required to be performed in order to administer the proper dose to each participant.

7.5.2 Handling, Storage and Accountability

The investigator or designee must confirm appropriate temperature conditions have been maintained during transit for all study treatment received and any discrepancies are reported and resolved before use of the study treatment.

Only participants enrolled in the study may receive study treatment and only authorized site staff may supply or administer study treatment. All study treatments must be stored in a secure, environmentally controlled, and monitored (manual or automated) area in accordance with the labeled storage conditions with access limited to the investigator and authorized site staff.

The investigator, institution, or the head of the medical institution (where applicable) is responsible for study treatment accountability, reconciliation, and record maintenance (ie, receipt, reconciliation, and final disposition records).

For all trial sites, the local country Sponsor personnel or designee will provide appropriate documentation that must be completed for drug accountability and return, or local discard and destruction if appropriate. Where local discard and destruction is appropriate, the investigator is responsible for ensuring that a local discard/destruction procedure is documented.

The trial site is responsible for recording the lot number, manufacturer, and expiry date for any locally purchased product as per local guidelines unless otherwise instructed by the Sponsor.

The investigator shall take responsibility for and shall take all steps to maintain appropriate records and ensure appropriate supply, storage, handling, distribution and usage of study treatments in accordance with the protocol and any applicable laws and regulations.

7.6 Treatment Compliance

Study intervention will be administered by the investigator and/or study staff according to the specifications within the Pharmacy Manual.

Interruptions from the protocol specified treatment plan for greater than 3 weeks between study treatments for situations other than treatment-related AEs such as medical / surgical events or logistical reasons not related to study treatment require consultation between the investigator and the Sponsor and written documentation of the collaborative decision on participant management.

7.7 Concomitant Therapy

Medications or vaccinations specifically prohibited in the exclusion criteria are not allowed during the ongoing trial. If there is a clinical indication for any medication or vaccination specifically prohibited during the trial, discontinuation from trial therapy or vaccination may be required. The investigator should discuss any questions regarding this with the Sponsor Clinical Director. The final decision on any supportive therapy or vaccination rests with the investigator and/or the participant's primary physician. However, the decision to continue the participant on study treatment requires the mutual agreement of the investigator, the Sponsor and the participant.

Listed below are specific restrictions for concomitant therapy during the course of the trial:

- Antineoplastic systemic chemotherapy or biological therapy
- Immunotherapy not specified in this protocol
- Chemotherapy not specified in this protocol
- Investigational agents other than pembrolizumab

- Radiation therapy
- Live vaccines within 30 days prior to the first dose of study treatment and while participating in the trial. Examples of live vaccines include, but are not limited to, the following: measles, mumps, rubella, varicella/zoster (chicken pox), yellow fever, rabies, Bacillus Calmette-Guérin, and typhoid vaccine. Seasonal influenza vaccines for injection are generally killed virus vaccines and are allowed; however, intranasal influenza vaccines (eg, FluMist[®]) are live attenuated vaccines and are not allowed.
- Systemic glucocorticoids for any purpose other than to modulate symptoms from an AE that is suspected to have an immunologic etiology. The use of physiologic doses of corticosteroids may be approved after consultation with the Sponsor.

Note: Use of prophylactic corticosteroids to avoid allergic reactions (eg, IV contrast dye or transfusions) is permitted.

Note: The use of intermittent inhaled steroids or intranasal or local injection of corticosteroids is permitted.

Participants who, in the assessment by the investigator, require the use of any of the aforementioned treatments (excluding the exceptions noted above) for clinical management should be removed from the trial. Participants may receive other medications that the investigator deems to be medically necessary.

All treatments that the investigator considers necessary for a participant's welfare may be administered at the discretion of the investigator in keeping with the community standards of medical care. All concomitant medication will be recorded on the eCRF including all prescription, over-the-counter products, herbal supplements, and IV medications and fluids. If changes occur during the trial period, documentation of drug dosage, frequency, route, and date should also be included on the eCRF.

All concomitant medications received within 30 days prior to the first dose of study treatment and up to 30 days after the last dose of study treatment should be recorded. Concomitant medications administered 30 days after the last dose of study treatment should be recorded for SAEs and ECIs as defined in Section 9.3.

Medications intended solely for supportive care (ie, antiemetics, analgesics, megestrol acetate for anorexia) are allowed. The exclusion criteria describe other medications that are prohibited in this trial. There are no prohibited therapies during the posttreatment Follow-up phase.

